24. ANAL PAP SMEAR

[OPTIONAL EXPLANATION: An anal Pap smear will be taken. This is like a cervical Pap smear. A Q-tip type swab will be inserted into the anus by the doctor or nurse practitioner to obtain cells that will be sent to the laboratory to check for abnormalities.]

| Statement | Strongly disagree | Slightly disagree | Neutral | Slightly agree | Strongly agree | Decline to answer |
|----------------------------------------|-----------------------------|-----------------------------|---------|--------------------------|--------------------------|-------------------|
| I am concerned about pain. | 1 | 2 | 3 | 4 | 5 | 99 |
| I feel the exam will be uncomfortable. | 1 | 2 | 3 | 4 | 5 | 99 |
| I feel at ease. | 1 | 2 | 3 | 4 | 5 | 99 |
| I am prepared to have the procedure. | 1 | 2 | 3 | 4 | 5 | 99 |

25. ONLY FOR VISITS 3 AND 5

HIGH RESOLUTION ANOSCOPY

[OPTIONAL EXPLANATION: High resolution anoscopy is done with use of a plastic tube instrument inserted in the anus to look at the tissue under a special light to see if there are warts or other abnormalities in the anal area. Vinegar is used to make any abnormal areas show up better under the light.]

Any abnormalities seen will be biopsied, or removed, with a small cutting instrument (after more numbing medication is injected) to send to the laboratory for special analysis.]

| Statement | Strongly disagree | Slightly disagree | Neutral | Slightly agree | Strongly agree | Decline to answer |
|----------------------------------------|-----------------------------|-----------------------------|---------|-------------------|-------------------|----------------------|
| I am concerned about pain. | 1 | 2 | 3 | 4 | 5 | 99 |
| I feel the exam will be uncomfortable. | 1 | 2 | 3 | 4 | 5 | 99 |
| I feel at ease. | 1 | 2 | 3 | 4 | 5 | 99 |
| I am prepared to have the procedure. | 1 | 2 | 3 | 4 | 5 | 99 |

26. Which of the following examinations or procedures concerns you the **very most** today? (Choose one)

FOR VISITS 3 AND 5

| Code | Procedure |
|------|--------------------------|
| 0 | No concern |
| 1 | Anal Pap smear |
| 2 | High resolution anoscopy |
| 3 | Biopsy |
| 99 | Decline to answer |

FOR VISITS 2 AND 4

| Code | Procedure |
|------|-------------------|
| 0 | No concern |
| 1 | Anal Pap smear |
| 99 | Decline to answer |

HEALTH BEHAVIOR QUESTIONS

Now I am going to ask you a few questions about yourself.

[from ACTG self report, questions E, H, QL0742(A5257)/ 12-31-08]

27. Are you on HIV medication(s)?

| No (skip to question 29) | Yes | Unsure/ Don't know |
|-----------------------------|-----|-----------------------|
| 0 | 1 | 98 |

28. Rate your **ability** to take all of your HIV medications as specifically prescribed.

| Very poor | Poor | Fair | Good | Very good | Excellent | N/A | Unsure/ Don't know | Decline to answer |
|--------------|------|------|------|--------------|-----------|-----|--------------------------|----------------------|
| 1 | 2 | 3 | 4 | 5 | 6 | 97 | 98 | 99 |

SMOKING QUESTIONS

29. Have you smoked cigarettes in the past 6 months?

| No (skip to question 31) | Yes |
|-----------------------------|-----|
| 0 | 1 |

AMC Smoking

30. On average over the past 6 months, how many cigarettes have you smoked per day? (1 pack equals 20 cigarettes)

_____ (number of cigarettes)

COST/TRANSPORTATION QUESTIONS

31. Which one best describes your hourly wage or annual income?

| Hourly Wage | Annual Income |
|------------------------|--------------------------|
| \$0.00 - \$4.99 | \$0.00 - \$9,999 |
| \$5.00 - \$7.25 | \$10,000 - \$14,999 |
| \$7.26 - \$9.99 | \$15,000 - \$19,999 |
| \$10.00 - \$14.99 | \$20,000 - \$29,999 |
| \$15.00 - \$19.99 | \$30,000 - \$39,999 |
| \$20.00 - \$24.99 | \$40,000 - \$49,999 |
| \$25.00 - \$29.99 | \$50,000 - \$59,999 |
| \$30.00 - \$34.99 | \$60,000 - \$69,999 |
| \$35.00 - \$39.99 | \$70,000 - \$79,999 |
| \$40.00 - \$49.99 | \$80,000 - \$99,999 |
| More than \$50.00/hour | More than \$100,000/year |

32. Did you miss work today for this visit?

| No | Yes |
|----|-----|
| 0 | 1 |

33. How did you get to the clinic today?

| Response | Code |
|----------------------------------------------------------------|------|
| Drive yourself | 1 |
| Get a ride from someone else in a personal vehicle | 2 |
| Take public transportation such as the metro bus or metro rail | 3 |
| Take a taxi | 4 |
| Walk or ride bike, or | 5 |
| Get there some other way (SPECIFY) _____ | 6 |
| Decline to answer | 99 |

34. If you took private/public transportation, what was the fare? \$_____

35. How much time (including travelling time) will you miss from your usual activities because of this appointment?

| Response | Code |
|-------------------------------------------|------|
| Less than 15 minutes | 1 |
| 15 to 30 Minutes | 2 |
| 31 Minutes to 60 Minutes (1 Hour) | 3 |
| 61 Minutes to 90 Minutes | 4 |
| 91 Minutes to 120 Minutes (2 Hours) | 5 |
| 120 Minutes to 180 Minutes (2 to 3 Hours) | 6 |
| 180 Minutes to 240 Minutes (3 to 4 Hours) | 7 |
| 240 Minutes to 300 Minutes (4 to 5 Hours) | 8 |
| 300 Minutes to 360 Minutes (5 to 6 Hours) | 9 |
| More than 360 Minutes (More than 6 Hours) | 10 |

36. How far did you travel for this appointment? _____ miles

37. If you drove, how much do you expect to pay for the parking? \$_____

| |
|----|
| NA |
| 99 |

38. If you are accompanied to your appointment by someone who missed work, what is the gender and age of this person?

| Accompanied | | | Not accompanied |
|-------------|--------|-----|--------------------|
| Male | Female | Age | 0 |
| 1 | 2 | | |

39. Did you have to get a caretaker today to attend to your children and/or an adult person living in your household in order to come to your appointment?

| No (Questionnaire complete) | Yes |
|--------------------------------|-----|
| 0 | 1 |

40. How much do you expect to pay the caretaker for today? (If no payment, skip to next question)

\$_____

41. Did the caretaker miss work in order to help you?

| No | Yes |
|----|-----|
| 0 | 1 |

42. What is the gender and age of the caretaker?

| Male | Female | Age |
|------|--------|-----|
| 1 | 2 | |

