4.3.5 Research staff administered questionnaires

A member of the research staff will administer a questionnaire to the study participant at each study visit to determine her smoking status, recent sexual history, as well as questions to assess quality of life, acceptability of the procedure, ascertain costs to the participant associated with anal cancer screening. The estimated time to complete this questionnaire is 20 minutes. The questionnaire includes the EQ-5D-5L for quality of life,⁴¹ PHQ-4 for anxiety and depression,⁴² the faces rating scale,⁴³ medication adherence,⁴⁴ acceptability of screening procedures,⁴⁵ sexual behaviors,²⁹ and personal health care cost information,⁴⁶ as well as adapted questions on self reported HIV medication adherence⁴⁶ and women's experience with colposcopy.⁴⁶ The baseline questionnaire ([Appendix XIII](#)) is administered at visit 1. The follow-up questionnaire (an abbreviated version of the baseline questionnaire) is administered at each subsequent visit (see [Appendix XV](#)).

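### The time-missed item on both questionnaires has overlapping bands from 2 hours up, the fare and miles items give no trip scope, and research time is not separated, so participant cost data are ambiguous, with no fixed direction for total cost

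*Combined protocol and SAP*

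**What the plan says.** Section 4.3.5 says the staff-administered questionnaire is meant, among other things, to "ascertain costs to the participant associated with anal cancer screening". Objective 2.3.2, which is exploratory, is to collect cost and time data for an economic evaluation. Section 7.2.2 passes these data on in a de-identified dataset for that work.

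The time item (Appendix XV Q35; Appendix XIII Q45) asks: "How much time (including travelling time) will you miss from your usual activities because of this appointment". The bands run cleanly up to code 5, "91 Minutes to 120 Minutes (2 Hours". From there they share endpoints: "120 Minutes to 180 Minutes (2 to 3 Hours", "180 Minutes to 240 Minutes (3 to 4 Hours", "240 Minutes to 300 Minutes (4 to 5 Hours", then 300 to 360 minutes. The last band starts above 360 minutes and does not overlap.

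The distance item (Appendix XV Q36; Appendix XIII Q46) asks: "How far did you travel for this appointment". The fare item (Q34; baseline Q44) asks what the fare was. Neither says one-way or return.

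On the length of the questionnaire, Section 4.3.5 states: "The estimated time to complete this questionnaire is 20 minutes".

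**The concern.** Three features of these items leave the recorded cost open to more than one reading.

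- **Bands.** Participants estimate in advance how much time they will miss, and such estimates plausibly come in whole hours. Whole hours from 2 to 5 are exactly the values that fit two codes. The label on code 5 hints at where 2 hours belongs; nothing does so for 3, 4 or 5 hours.
- **Trip scope.** One participant may give the trip in and another the round trip, and the form would not show which.
- **Research time.** The appointment is a study visit. It includes the questionnaire, extra swabs for central HPV testing and for Arbor Vita, and random biopsies when fewer than two directed ones are taken. None of this time is recorded separately, although the target is the cost of screening.

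The economic analyst receives codes in a de-identified dataset and cannot readily go back to ask. If sites settled on different conventions for whole hours, the difference would look like a difference between sites.

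**Working it through.** The documents state no cost or time estimate for these items, so there is no plan figure to reproduce. The inputs are the printed bands, the stated 20 minutes, and the wage-band edges on the forms. Visit durations and fares are assumptions.

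**1. Which answers fit two codes.** Checking each endpoint against all bands: 15, 30, 60, 90 and 360 minutes each fit one code. The answers 120 (codes 5 and 6), 180 (6 and 7), 240 (7 and 8) and 300 (8 and 9) each fit two.

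**2. Size of the ambiguity.** Midpoint = (lower + upper)/2. Code 5: (91 + 120)/2 = 105.5. Codes 6 to 9: 150, 210, 270, 330.

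| True answer (min) | Lower code midpoint | Upper code midpoint | Gap | Error against true time |
|---|---|---|---|---|
| 120 | 105.5 | 150 | 44.5 | -14.5 or +30 |
| 180 | 150 | 210 | 60 | ±30 (30/180 = 17%) |
| 240 | 210 | 270 | 60 | ±30 (30/240 = 12.5%) |
| 300 | 270 | 330 | 60 | ±30 (30/300 = 10%) |

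The gap as a share of the true time at 3, 4 and 5 hours is 60/180 = 33%, 60/240 = 25% and 60/300 = 20%. That is the disagreement between two coders, not the error of either.

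**3. What non-overlapping bands would do.** With 121-180, 181-240 and 241-300 the midpoints are 150.5, 210.5 and 270.5. Answers of 180, 240 and 300 minutes each get one code, but each is valued 29.5 minutes low. Re-cutting the bands buys consistency, not accuracy.

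**4. Research time.** With total time T, the 20-minute questionnaire is 20/T of the recorded time and inflates the remainder by 20/(T - 20).

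| Assumed T (min) | Share of recorded time | Inflation |
|---|---|---|
| 60 | 33% | 50% |
| 120 | 17% | 20% |
| 180 | 11% | 12.5% |
| 240 | 8% | 9% |
| 360 | 6% | 6% |

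**5. Net direction of total cost.** Take a wage of $7.25 an hour and an assumed $10 return fare recorded one-way and used as the total. Extra time is worth 7.25 × 20/60 = $2.42, the fare is $5.00 too low, and the net is 2.42 - 5.00 = -$2.58. At $15 an hour with no fare, the net is 15 × 20/60 = +$5.00. The sign depends on the wage and on how the fare was answered.

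**The case against.** The strongest reply is that this is a small matter in exploratory data, and that parts of it belong to the analysis rather than the form. Several points stand.

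- Whichever code is chosen, the true time lies inside the recorded band, so an analysis that treats the answers as intervals remains valid. The ambiguity matters for midpoint costing and for comparisons between sites.
- Asking for total time is legitimate. The stated 20 minutes can be subtracted without changing the form. Section 4.3.5 also calls the follow-up form an abbreviated version, so 20 minutes is probably an upper figure there.
- The costing rules of the economic evaluation are not in these documents, and Section 8.1 says recording instructions are issued separately. A tie rule or trip convention may exist elsewhere. Staff administer the questionnaire and can clarify answers. A site difference is therefore a risk, not a demonstrated fact.

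A reader might infer that participant cost as a whole is overstated. The documents do not support that. The overlap can push a code up or down. The fare and miles items are in the past tense, and the fare follows an item on how the participant reached the clinic, whereas parking and caretaker costs are asked as amounts she expects to pay. A one-way answer to fare or miles is thus quite natural, and used as a total it understates travel cost. A large shift in mean time per visit is likewise unsupported: it needs a known share of whole-hour answers, and the documents give none.

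What does not fall away is that both printed forms admit two codes for four likely answers and leave the trip scope open.

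**Conclusion.** The point holds as one of ambiguity. On both forms, answers of exactly 2, 3, 4 or 5 hours fit two codes. Their midpoints differ by 44.5 minutes (2 hours) or 60 minutes (3 to 5 hours), and at 3 to 5 hours either choice is 30 minutes off. Fare and miles may differ by a factor of two, direction unknown. Time alone is likely overstated relative to routine screening, by about 20 minutes for the questionnaire, if nothing is subtracted; no direction can be claimed for total cost.

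The sizes assume midpoint costing, and the percentages in the research-time table rest on assumed visit durations. How often whole-hour answers occur is unknown. The impact is confined to exploratory objective 2.3.2; the accuracy, prevalence and incidence analyses are untouched. The change is worth making because it is nearly free and an exact answer that was not recorded cannot be recovered later.

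**What to change.** - **Time (Q35 and baseline Q45):** record hours and minutes as a number. This removes both the tie and the midpoint error. If bands must stay, use 121-180, 181-240, 241-300, 301-360 and over 360 minutes, accepting that the midpoint error remains.
- **Fare and miles (Q34 and Q36; baseline Q44 and Q46):** state one-way or return in the item, with the same choice on both forms.
- **Research time:** specify that the economic analysis subtracts the stated 20 minutes, with a smaller deduction as a sensitivity analysis for the shorter follow-up form. This does not remove time spent on research swabs or random biopsies, which should be stated as a limitation.

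The cost is a wording change on two forms and one line in the costing rules. Answers already collected stay ambiguous. Old and new codings must be harmonised, for example by treating the old codes as intervals.
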